#### 6.3 Exercise intervention

During the study period, participants will be instructed to complete the muscle strengthening exercise routine twice a week for 12 weeks during the intervention, and to monitor one's total steps and active minutes. Personalized aerobic activity goals will be set and monitored via health coaches on the research study team. Participants will be assigned a study coordinator/health coach who will work with each participant over the course of the intervention. Study coordinators/health coaches will schedule weekly telehealth meetings with the participants for the first five weeks of the intervention, following the fifth week participants will be given the choice to continue meeting with their study coordinator/health coach weekly or transition to a tapered telehealth session schedule where they will meet with their study coordinator/health coach again during week 8 and week 11. At these health coaching sessions, a semi-standardized template will be used. Study coordinators will check in to determine study progress, help set and monitor exercise goals, systematically evaluate for adverse events, and will work to build rapport and support the participants on their exercise adoption and maintenance journey. Study coordinators/health coaches will also be instructed to assess for volume/intensity/difficulty of each of the exercises. These

sessions are done over video so that the coordinator can build rapport with participants, and that participants can show or demonstrate issues with exercises or their form. Participants will have access to a study-specific website with resources related to exercise prescription and exercise components (strivecardio-study.lab.uiowa.edu).

#### 7. Statistical Considerations

#### 7.1 Statistical Methods

The primary objective of this pilot study is to obtain preliminary evidence of changes in PWV with the comprehensive exercise program. A 1 m/sec decrease in PWV from pre- to post-intervention reflects a clinically relevant change as this has previously been shown to be associated with a 15% risk reduction in CVD events. In statistical terms, we are testing the null hypothesis  $H_0$ :  $\Delta_{Post-Pre} = 0$  versus the alternative hypothesis  $H_1$ :  $\Delta_{Post-Pre} \neq 0$ . Using a repeated measures design with 1 within subject factor (time: pre- and post-intervention), the design achieves 93% power to test for a time effect among 30 participants. We will recruit 33 participants to account for a potential 10% dropout rate to accommodate a final analytic sample size of 30. Power calculations are based on the following assumptions: standard deviation of 1.4, using an F test, 5% significance level, an autocorrelation of 0.5, and 15% drop out.

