# **Revision History**

# Version 1, Version Date 1/13/2025

Protocol Version	Date	Change Initiated (Initials)	Brief description of protocol modification/actions requested, if any
Version 1.0	06/05/2024	JG	Primary version
Version 1.1	07/03/2024	JG	Revising protocol for additional health history information, participant materials description
Version 1.2	09/27/2024	AB	Revising protocol to expand inclusion criteria, study population description
Version 1.3	10/11/2024	AB	Adding short performance physical battery measures
Version 1.4	11/15/2024	AB	Revising protocol to include recruiting participants from the Iowa Cancer Registry
Version 1.5	1/13/2025	JG	Removing [name] from the protocol, has left team
Version 1.6	2/10/2025	JG	Clarifying inclusion criteria regarding treatment resistant hypertension and adding triglycerides as one of our blood biomarkers
Version 1.7	4/15/2025	JG	Updating sample size to n=33 to account for 10% dropout for analytic sample size of 30

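### Section 7.1 assumes 15% dropout for the power but 10% for recruitment, and the stated 93% fits 30 enrolled better than 30 analysed

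*Protocol*

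**What the plan says.** All the relevant text but one entry is in Protocol section 7.1 (Statistical Methods).

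- Effect: "A 1 m/sec decrease in PWV from pre- to post-intervention reflects a clinically relevant change". The hypotheses that follow are two-sided, testing a mean change of zero against a non-zero change.
- Power: "the design achieves 93% power to test for a time effect among 30 participants".
- Recruitment: "We will recruit 33 participants to account for a potential 10% dropout rate to accommodate a final analytic sample size of 30".
- Assumptions: "Power calculations are based on the following assumptions: standard deviation of 1.4, using an F test", followed by "5% significance level, an autocorrelation of 0.5, and 15% drop out".

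The Revision History entry for version 1.7 reads "Updating sample size to n=33 to account for 10% dropout for analytic sample size of 30", which agrees with the recruitment sentence.

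**The concern.** One paragraph applies two dropout rates to the same single-arm, pre-post comparison of the primary endpoint: 15% for the power and 10% for the recruitment margin. Nothing marks them as alternative scenarios.

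This raises the question of what 30 means. If dropout is an input to the power calculation, 30 should be the number before dropout. The recruitment sentence makes 30 the number left after dropout. Both cannot be the basis of the 93%.

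The paragraph is the only justification of the sample size. As it stands, a reader cannot tell whether about 30 or about 28 participants are expected in the primary analysis, or which power goes with that number.

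**Working it through.** **Inputs, all from section 7.1**

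- SD σ = 1.4
- Correlation ρ = 0.5
- F test at 5%, two-sided by the stated alternative
- Dropout 15% (power assumptions) and 10% (recruitment)
- Effect δ = 1 m/s. This is an assumption: the paragraph calls it clinically relevant but does not list it among the power inputs.

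**Method.** A repeated-measures F test with two time points is equivalent to a two-sided paired t test.

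- SD of the change = σ√(2(1 − ρ)) = 1.4 × √(2 × 0.5) = 1.4. At ρ = 0.5 it does not matter whether 1.4 is the SD at each visit or the SD of the change.
- Noncentrality λ = nδ² / (2σ²(1 − ρ)) = n / 1.96, with degrees of freedom 1 and n − 1.
- Power = probability that a noncentral F(1, n − 1; λ) exceeds the 95th percentile of the central F(1, n − 1).

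**The plan's own figure first.** 30 enrolled less 15% leaves 30 × 0.85 = 25.5.

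| Analysed n | Where it comes from | λ | Power |
|---|---|---|---|
| 25 | 25.5 rounded down | 12.76 | 92.9% |
| 25.5 | 30 × 0.85 | 13.01 | 93.3% |
| 26 | 25.5 rounded up | 13.27 | 93.8% |
| 28 | 33 × 0.85 = 28.05 | 14.29 | 95.4% |
| 29.7 | 33 × 0.90 | 15.15 | 96.4% |
| 30 | stated analytic sample | 15.31 | 96.6% |

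The 93% is reproduced at 25 or 25.5. It is not reproduced at 30 analysed, where the gap is 96.6 − 93 = 3.6 points.

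**What would give 93% with 30 analysed?** Changing one input at a time, it takes an effect of about 0.91 m/s (0.90 to 0.92 for a power that rounds to 93%), an SD of about 1.54, or a correlation of about 0.4. Section 7.1 states none of these. At n = 30 a normal approximation (97.5%) and a one-sided test (98.5%) are further away still.

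**Recruitment needed for 30 analysed**

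- At 10% dropout: 30 / 0.90 = 33.3, so 34 by strict rounding up. The protocol's 33 equals 30 × 1.1 and yields 29.7.
- At 15% dropout: 30 / 0.85 = 35.3, so 36.

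**The case against.** The strongest objection is that only the conflict between 10% and 15% is certain. Reading 30 as enrolled in one sentence and analysed in the other depends on 1 m/s being the design effect, which the list of assumptions does not say. The match is also not tight: 26 completers would print as 94%, and a mixed model that keeps dropouts' baseline values (30 at baseline, 25 to 26 at follow-up) gives 93.8% to 94.5%. Finally, nothing in the conduct of the trial changes, because the stated power is a floor under either rate.

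Much of this stands. The meaning of 30 is an inference, though a well-supported one: listing dropout as a power input implies a number before dropout, 1 m/s is the only effect given, and together they return the stated 93%. The mixed-model variant loosens the match only slightly, since section 7.1 says the power rests on an F test. If 1 m/s is not the design effect, the two rates still conflict and the power claim then has no stated effect behind it.

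The lack of practical harm is a reason to rate the point minor. It is not a reason to leave the paragraph as it is.

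**Conclusion.** The point holds and is minor. Two dropout rates in one paragraph contradict each other on the face of the text.

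Taking 1 m/s as the design effect, with SD 1.4, correlation 0.5 and a two-sided 5% test, the stated 93% belongs to 30 enrolled with 15% lost. It understates the power for 30 analysed by about 3.6 points.

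The error is conservative. With 33 recruited, power is about 96% at 10% dropout and about 95% at 15%. The trial is not underpowered, and more enrolment is not needed to meet the stated 93%.

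**What to change.** Name the design effect among the power assumptions (1 m/s if the sponsor confirms it), keep one dropout rate, state the number analysed, and give the power that goes with it.

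- **If 10% is intended**, as the version 1.7 entry indicates: remove the 15% from the assumptions and write, for example: *We will recruit 33 participants; with 10% dropout about 30 will be analysed (33 × 0.90 = 29.7), giving about 96% to 97% power to detect a 1 m/s change (SD 1.4, correlation 0.5, F test, two-sided 5%).*
- **If 15% is intended with 33 recruited**: replace the 10% and the analytic sample of 30 with about 28 analysed and about 95% power.
- **If 15% and a full 30 analysed must both be kept**: 33 is too few and 36 would be needed (36 × 0.85 = 30.6). Reaching the stated 93% does not require this.

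The first two options cost one reworded paragraph, with no extra participants and no change to the analysis. Only the third adds participants (3).

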#### 7.2 Statistical Analysis

#### 7.2.1 General Approach

Continuous variables will be summarized using descriptive statistics such as mean, standard deviation, median, minimum, and maximum. Categorical variables will be summarized by count and proportion.

#### 7.2.2 Analysis of Primary Endpoint(s)

PWV

The within patient change in PWV will be assessed from pre- to post-intervention. Mixed effects regression models will be used to estimate changes in PWV. Random effects will be included to account for the longitudinally correlated nature of repeat measurements within a patient. Estimated mean changes and associated 95% confidence intervals will be reported.

#### 7.2.3 Analysis of Secondary and Exploratory Endpoint(s)

**FMD** 

The within patient change in FMD will be assessed from pre- to post-intervention. Mixed effects regression models will be used to estimate changes in FMD. Random effects will be included to account for the longitudinally correlated nature of repeat measurements within a patient. Estimated mean changes and associated 95% confidence intervals will be reported.

#### ASCVD Risk

The within patient change in the modifiable components of the ASCVD Risk score (total cholesterol, HDL cholesterol, and systolic blood pressure) will be assessed from pre- to post-intervention. Mixed effects regression models will be used to estimate changes in total cholesterol, HDL cholesterol, and

systolic blood pressure. Random effects will be included to account for the longitudinally correlated nature of repeat measurements within a patient. Estimated mean changes and associated 95% confidence intervals will be reported.

#### Functional Fitness

Mixed effects regression models will be used to estimate changes in each of the 6 tests included in the Functional Fitness Test from pre- to post-intervention. Random effects will be included to account for the longitudinally correlated nature of repeat measurements within a patient. Estimated mean changes and associated 95% confidence intervals will be reported.

#### Muscle Strengthening Exercise Session Adherence

Exercise session adherence will be defined as the proportion of planned exercise sessions in which a participant completes at least 50% of the prescribed exercises. The mean and associated 95% confidence interval will be reported.

#### Aerobic Physical Activity Adherence

Aerobic physical activity adherence will be defined as the proportion of planned weeks a participant accumulates 150 minutes of moderate intensity activity. The mean and associated 95% confidence interval will be reported.

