#### STUDY SCHEMA

Five weeks of weekly health coaching followed by either:

• Tapered health coaching (sessions only during weeks 8 and 11)

OR

• Continued weekly health coaching (sessions continue weekly through week 12)

Twelve weeks of home-based exercise including:

- two days/week of full-body muscle strengthening exercises
- · Aerobic activity aiming to achieve 150 mins/week

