# 3. Study Objectives and Endpoints

OBJECTIVES	ENDPOINTS
Primary	
-To evaluate changes in PWV following a 12-week home-based aerobic and muscle strengthening exercise program	-Within participant change from pre- to post- intervention as measured by carotid-femoral pulse wave velocity (PWV)
Secondary	
To evaluate changes in FMD following a 12-week home-based aerobic and muscle strengthening exercise program	-Within participant change from pre- to post- intervention as measured by brachial artery flow mediated dilation (FMD)
-To evaluate changes in the modifiable components of the ASCVD risk score (total cholesterol, HDL cholesterol, triglycerides, and systolic blood pressure) following the 12-week home-based comprehensive exercise program	-Within participant change of total cholesterol, HDL cholesterol, triglycerides, and systolic blood pressure from pre- to post-intervention
-To evaluate changes in functional fitness	-Within participant change of functional fitness from pre- to post-intervention as measured by the Functional Fitness Test
-To estimate muscle strengthening exercise session adherence	-Proportion of planned exercise sessions in which a participant completes at least 50% of prescribed exercises
-To estimate adherence to the aerobic physical activity guidelines (150 minutes/week)	-Proportion of planned weeks a participant accumulates 150 minutes of moderate intensity activity per week
-To estimate tele-coaching adherence	-Proportion of planned coaching sessions in which a participant completes
-To estimate acceptability	-Likert scale ratings of quality of exercise equipment, educational materials, health coaching, study feedback and distance delivery format
-To estimate changes in anthropometrics	-Within participant changes of waist and hip circumference, and weight from pre- to post-intervention
-To estimate changes in ambulatory activity levels	-Within participant change in average daily steps taken within a week from pre- to post-intervention as measured via ActiGraph accelerometer
-To estimate changes in psychosocial behavior change measures	-Within participant change of questionnaire scores (SEE, BPNES, PSS, BREQ-3) from pre- to post-intervention
-To estimate changes in diet	-Within participant change of questionnaire score (Multifactor Screener in Observing Protein and Energy Nutrition (OPEN)) from pre- to post- intervention

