#### 4.2 Exclusion criteria

⊏XCIU	ision Criteria
1	Absolute contraindications to exercise (i.e., acute myocardial infarction, severe
orthor	pedic or musculoskeletal limitations)
2	History of previous myocardial infarction, ischemia, or hemorrhagic stroke
3	Medically documented history of heart disease including heart valve disease, coronary
artery	disease, heart failure, peripheral artery disease, aortic disease, pericardial disease,
cereb	rovascular disease, or deep vein thrombosis
4	Medical documentation of treatment-resistant hypertension OR taking 3 or more anti-

hypertensives with persistent hypertension

Medically documented history of cardiovascular disease including (but not limited to):
bypass surgery, stent procedures, bypass grafts, or coronary angioplasty

6 Medically documented or self-reported type 1 diabetes (insulin-dependents) Prescriptions for or use of semaglutide (GLP-1 agonists) including name brands: Ozempic, Wegovy or Mounjaro Current or recent (within last 3 months) use of hormone replacement therapy (HRT) Evidence of recurrent or metastatic disease Currently performing resistance training ≥2 days per week 10 11 Currently exceeding 150 minutes of at least moderate intensity exercise per week 12 Report of chest pain, shortness of breath, fainting, or angina pectoris 13 Self-reported history of falling, fall risk Have physical disability that would limit range of motion through exercises such as 14 sitting, standing and inability to walk one block Plans to move from the area 16 Enrolled in another clinical trial or has used of any investigational drugs, biologics, or devices within 30 days prior to study enrollment Self-reported tobacco use in last 7 days, current smoking, current tobacco use including e-cigarettes and vaping devices 18 Not suitable for study participation due to other reasons at the discretion of the investigator

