#### 5. Study Design and Methods

#### 5.1 General Design

- A single arm exercise study
- The intervention itself is 12 weeks of exercise, with one week of accelerometer wear prior to
  exercise with an additional week to schedule post-study visit procedures, yielding a total
  intervention length of 14 weeks.
- The exercise intervention will consist of (a) in-person pre-intervention study measures; (b) instructional materials (e.g. detailed exercise manual) and exercise training equipment (e.g. resistance bands, adjustable pair of dumbbells, Fitbit Charge 5); (c) a virtually delivered instructional session; (d) access to informational web materials; (e) support and feedback provided via virtual health coaching sessions; and (f) in-person post-intervention study measures. Participants will also receive access to a study specific website (strivecardio-study.lab.uiowa.edu) that will include online versions of resources including video demonstrations, device support, exercise recommendations and study components.
- Health coaching sessions will be delivered virtually and consist of (a) an initial health coaching session during week one discussing the participant's visions for health and wellness and overall goals of completing the intervention exercises; (b) sessions delivered once per week through week four discussing progress, barriers, facilitators, self-efficacy, and motivations for exercise goals to facilitate exercise adoption; (c) a midpoint check-in including a non-bias report from their health coach describing their progress thus far in the intervention. Participants then have the personal option to continue meeting with their health coach on a weekly basis or taper their health coaching sessions to include only weeks eight and eleven; (d) a final in person health coaching session to conclude.

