SPPB. The short performance physical battery (SPPB) is a series of functional mobility assessments which measure balance, lower extremity strength, and fitness. Developed by the National Institute of Aging, the SPPB has clinically useful implications of predicting physical decline in older adults. The full battery utilizes standardized scoring, for a minimum of 0 points, to a maximum of 12 points, and includes the following three subscales: 1.) **Balance**. Each participant will stand for 10 seconds with their feet together, 10 seconds with their feet placed semi-tandem, and a final 10 seconds with their feet fully tandem. Participants receive a score from 0-4, based on their ability to attempt each position. 2.) **Repeated chair stand**, measuring lower extremity strength. Participants will stand up and sit down five times as quickly as they can. Participants receive a score of 0-4, based on total duration it takes to complete five total repetitions. 3.) **Gait speed**. Each participant will walk to a line placed on the floor three meters away at their typical walking pace. Participants receive a score from 0-4, based on total duration of walking this distance. **When collected:** Baseline, final visit (~14 weeks).

Exercise adherence. Adherence to intervention exercises will be measured via detailed exercise logs. A participant needs to complete at least 50% of the prescribed exercises in a session to be considered adherent to the session. **When collected:** ongoing, logs will be completed throughout the intervention and submitted at the final visit. Additionally, we will be monitoring participant's Fitbit data via Fitabase over the course of the study to monitor total physical activity and minutes of strength training logged.

Health coaching adherence. Adherence to health coaching will be monitored by the health coach on a weekly basis. A health coaching will be considered complete if the participant attends and participates in the health coaching session. Health coaches will also record the modality in which the session was completed, as well as the duration of completed sessions in minutes. **When collected:** ongoing, health coaches will record in REDCap whether a health coaching session was completed or not following each scheduled session.

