# Appendix 2: Aerobic Exercise tracking log (example) for week 1 of 12 weeks

								QR
Participant:		AEROB	IC EXER	CISE LO	G			CODE
WEEK OF INTERVENTION: 1	Dates: _	/	/		/	/	_	HERE

Day of	Light intensit	ty	Moderate inter	nsity	Vigorous inter	Total daily steps	
week	Activities	Total minutes	Activities Total minute		Activities	Total minutes	(Fitbit)
Example	Mall shopping	60	Walking the dog Bike ride	50	NONE	0	5,000
1							
2							
3							
4							
5							
6							
7							

\*\*Record aerobic activities under the best fit intensity and record the total minutes you spent in each intensity. For example, in one day if you spent 30 minutes walking the dog and later spent 20 minutes on a bike ride both activities would be recorded under moderate intensity and the total duration is 50 minutes.

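### The aerobic adherence endpoint credits only moderate-intensity minutes, so read literally it fails weeks that reach 150 minutes once separately logged vigorous minutes are added

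*Protocol*

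**What the plan says.** The protocol defines the endpoint twice, in nearly the same words. Section 7.2.3 (Aerobic Physical Activity Adherence) says: "Aerobic physical activity adherence will be defined as the proportion of planned weeks a participant accumulates 150 minutes of moderate intensity activity". The endpoint table in Section 3 says: "Proportion of planned weeks a participant accumulates 150 minutes of moderate intensity activity per week". Neither entry mentions vigorous minutes.

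Three other places use the same 150-minute quantity without restricting it to moderate intensity:

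- The Study Schema gives the intervention target as "Aerobic activity aiming to achieve 150 mins/week".
- The Section 3 objective paired with this endpoint begins "To estimate adherence to the aerobic physical activity guidelines (150 minutes/week" and names no intensity.
- Exclusion criterion 11 in Section 4.2 reads "Currently exceeding 150 minutes of at least moderate intensity exercise per week", so vigorous minutes count at entry.

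On data, Section 6.1 says: "Adherence to intervention exercises will be measured via detailed exercise logs". The aerobic log in Appendix 2 has separate columns for light, moderate and vigorous minutes. It tells participants: "Record aerobic activities under the best fit intensity and record the total minutes you spent in each intensity". Section 7.2.3 reports the endpoint as a mean with a 95% confidence interval.

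**The concern.** The log puts each activity under one intensity, so minutes judged vigorous never reach the moderate column. An analyst who applies the stated definition to the log reads the moderate column alone. A week can then be scored as not met although the participant reached the weekly aerobic target, partly at a higher intensity. The endpoint would not measure the objective it is paired with, and the protocol would use two units for the same quantity, one at entry and one at outcome.

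What is at stake is how the delivered aerobic dose is described. In a single-arm pilot meant to inform a larger grant application, the adherence figure helps readers judge whether the programme was carried out. A figure that omits qualifying minutes could be taken for under-delivery.

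**Working it through.** The protocol gives no expected rate, sample size or power for aerobic adherence, so there is no stated figure to reproduce. The check is to score weeks under the rule as written and under the wording used at entry.

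**Inputs from the protocol**
- Threshold: 150 minutes per week (Sections 3 and 7.2.3).
- Rule as written: moderate minutes ≥ 150.
- Rule in the sense of exclusion 11: moderate + vigorous minutes ≥ 150.
- Weeks in the denominator: 12 (Section 5.1: "The intervention itself is 12 weeks of exercise").
- Analytic sample: 30 (Section 7.1).

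**Step 1: single weeks.** The minute mixes are illustrative assumptions.

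| Moderate | Vigorous | Sum | As written | Moderate or above |
|---|---|---|---|---|
| 150 | 0 | 150 | met | met |
| 150 | 60 | 210 | met | met |
| 120 | 30 | 150 | not met | met |
| 100 | 60 | 160 | not met | met |
| 75 | 75 | 150 | not met | met |
| 0 | 150 | 150 | not met | met |

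The rules disagree only when moderate minutes are below 150 and vigorous minutes close the gap. No week passes as written and fails under the inclusive rule, because adding vigorous minutes cannot reduce the sum. Any discrepancy therefore lowers the adherence estimate.

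**Step 2: one participant.** Suppose k of her 12 weeks are 110 moderate + 50 vigorous minutes (160 in all) and the rest have at least 150 moderate minutes. Adherence as written is (12 − k)/12, which for k = 0, 3, 6, 9 and 12 gives 100%, 75%, 50%, 25% and 0%. Under the inclusive rule it is 100% in every case.

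**Step 3: the group mean.** With 30 participants and 12 weeks each, the mean falls by (affected participant-weeks)/(30 × 12). The number affected is not in the protocol, so these are assumed scenarios:

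- No affected weeks: 0/360 = 0 points.
- 3 women × 3 weeks: 9/360 = 2.5 points.
- 5 women × 6 weeks: 30/360 = 8.3 points.
- 6 women × 9 weeks: 54/360 = 15 points.

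These show how the arithmetic scales. They are not forecasts.

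**The case against.** The strongest reply is that nothing in the protocol says outright that vigorous minutes are discarded. Read with its objective and the schema, the moderate-intensity phrase could be meant as a floor, and combining log columns is the sort of detail a statistical analysis plan often settles. The data path is also not fully stated: the Appendix 2 log is labelled an example, Section 6.1 spells out only the strength-session rule, and Fitbit data are monitored as well.

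Part of this stands. The zero credit follows from the literal text, and a sensible analyst might add the columns anyway. But the protocol does not leave the definition open. It fixes it in two places, and an analysis plan that added vigorous minutes would depart from that wording. Section 6.1 names logs as the source for exercise adherence, and the only aerobic log shown separates the intensities.

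The effect may also be very small. Women already above 150 minutes a week at entry are excluded, and no progression to vigorous aerobic work is prescribed; the progressions in Table 2 are for strength exercises. The ten-woman first-year study reported 89% aerobic compliance (definition not given), which does not suggest large losses. This stands in full and limits the point to a wording correction.

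Two stronger readings are tempting but unsupported. A reader might infer that women who train harder are classed as non-adherent. The endpoint is a proportion of weeks per participant, and a woman with 150 or more moderate minutes keeps the week whatever else she does. A reader might also infer that the bias is greatest in the fittest women or grows in later weeks. The protocol says nothing about who will do vigorous activity or when.

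**Conclusion.** The point holds as a stated scoring rule that does not match its own objective. Taken literally, Sections 3 and 7.2.3 fail a week with fewer than 150 moderate minutes even when moderate plus vigorous minutes reach 150. That conflicts with the schema target, the paired objective and exclusion 11.

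The direction is certain: relative to a count of all minutes at moderate intensity or above, the estimate can only be too low. The size is unknown. It depends on how many weeks combine under 150 moderate minutes with enough vigorous minutes to close the gap, and the count could be zero. The conclusion assumes that the definition is applied as written to a log structured like Appendix 2.

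The consequence is limited. The endpoint is secondary and descriptive, with no test or success threshold attached, and the PWV analysis and its power are untouched. The correction is worth making because the present wording is inconsistent and easily repaired.

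**What to change.** In the Section 3 endpoint table and in Section 7.2.3, define an adherent week as one with at least 150 minutes of activity at moderate intensity or above, calculated as the moderate plus vigorous columns of the Appendix 2 log with each minute counted once. This uses the same intensity floor as exclusion 11. Counting each minute once follows the schema and objective, which state plain minutes. Giving vigorous minutes extra weight would be a different rule, and the protocol supplies no basis for it.

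The cost is one wording change in two places. The vigorous minutes are already logged, so no new data or visits are needed. The change affects endpoint scoring only and leaves the exercise prescription as it is.
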